Screening Procedures: The Study Clinician administers the substance use disorders section of the Mini International Neuropsychiatric Interview (MINI) to confirm DSM-V AUD and to assess for other potential substance use disorder diagnoses, any suicidal ideation in the past 7 days, plan or intent past 6 months, or suicide attempt past year, and homicidal ideation with plan and intent in the past 30 days (see *Study Instruments Table* below for an overview of assessment measures and materials). Recent drinking will be determined during the AUD assessment to determine whether participants meet drinking inclusion requirements. Presence of at least mild craving will be assessed via the self-report instrument "Pennsylvania Alcohol Craving Scale (PACS);" a score of at least 10 is required. Participants undergo a complete medical history and a physical examination with the Study Clinician. Participants who are found to be in good medical health from the initial exam complete the Clinician-Administered PTSD Scale for DSM-5 (CAPS) —to determine current PTSD diagnostic status. Participants complete a self-report demographic questionnaire that includes a forced choice item regarding their goals for their alcohol use over the next month (i.e., no change, reduce or cut down on amount of drinking, abstain completely). Those who indicate no desire to change their drinking are excluded from the study.

Those who are found to be initially eligible are asked to complete a short battery of self-report measures regarding craving, PTSD symptom severity, and characteristics that may moderate response to prazosin and naltrexone.

Data Capture: The interview data are recorded on paper or entered directly into an ACCESS database and self-report measures are entered online into a Survey Monkey form. Research staff remain in the room with participants while they complete the self-report measures to ensure that they do not leave the Survey Monkey website. Note: there are paper forms available in the event there is a problem with either the ACCESS or Survey Monkey systems or if a participant prefers to complete measures off-line.

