provocative reading material and puzzle books prior to completing the second induction, the procedures of which parallels the first.

Study Medications

Prazosin: Prazosin HCl or identical matched placebo capsules are dispensed as 1, 2, and 4 mg capsules prepared by Kelley-Ross Pharmacy, a compounding pharmacy in Seattle. A 25mg riboflavin trace will be added to each capsule to evaluate medication compliance.

Naltrexone: 50 mg naltrexone or identical matched placebo capsules prepared by Kelley-Ross Pharmacy (tablets are ground and then compounded with the 25mg riboflavin trace).

Procedures for Maximizing Research Integrity

Maintaining the Study Blind: Only the VAPSHCS research pharmacist will have access to the randomization schedule, and she will have no contact with study participants. The blind may be broken by the PIs in case of safety concerns and for the purposes of interim analyses, but the information will not be shared with study staff except in the event of clinically significant safety concerns.

Maximizing Retention: We update contact information at each clinical and assessment visit. Participants will be paid \$15 for each of the two blood draws.

Study Instruments

Study Construct/ Variables	Study Phase	Purpose
Inclusion/Exclusion Criteria and Blocking Factors		
Demographic information	V1	sample description, blocking (gender)
Medical history interview	V1	exclusion
Medical Exam	V1, V8	exclusion; safety
Lab values MINI International Psychiatric Interview (DSM-V AUD & SUD onset of drinking and alcohol problems as well as recent drinking; DSM-IV Psychosis; suicidality, homicidality)	V1, V8 V1	exclusion; safety inclusion and exclusion
Alcohol use goal (embedded in MINI AUD)	V1	inclusion, blocking, treatment moderator
Desires for Alcohol Questionnaire (DAQ)	V2, V8	, outcome
Life Events Checklist	V1, V8	blocking
Penn Alcohol Craving Scale	V1, V2, V8	inclusion
Clinician-Administered PTSD Scale For DSM-5 (CAPS)	V1, V8	blocking, treatment moderator (Aim 3)
Tracking		
Contact form	V1-V7	retention
Primary Outcomes		
Alcohol Biomarker (Peth)	V1, V8	outcome
Alcohol Craving (DAQ)	V8	outcome (Aim 2)
Alcoholuse	V8	outcome (Aim 2)
Reward Craving for Craving Inductions from DAQ	V8	outcome (Aim 1)
Relief Craving for Craving Inductions from DAQ	V8	outcome (Aim 1)
Hypothesized Moderators		
State Trait Anxiety	V1, V8	moderation (Aim 3)
Anxiety Sensitivity Inventory	V1, V8	moderation (Aim 3)

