The transferred data will not have any identifying information connected with them. They will be raw data numbers only identified by a study code number. Inadvertent disclosure of any of these data will not have any impact on participants, as a third party would not be able to discern what the data are. The study crosswalk, the bridge between the study code and participant's name, will be kept in the project folder in the VA secure network (\\R01PUGHSM03.R01.MED.VA.GOV\Research\[name]\IVR_Studies\00623 (AA-PaN Study)\11 - Tracking & Databases) and will not be shared with [name].

Statistical Analysis Plan

Statistical analysis will focus on three primary outcomes and a secondary outcome (average drinks per drinking day). The three primary outcomes are Percent Drinking Days (PDD), Percent Heavy Drinking Days (PHDD), and craving scores from PACS. The Form-90 will be used to gather drinking data for the three months prior to receipt of study medication as well as the six-weeks of study medication. This information will be used to compute PDD, PHDD, and average drinks per drinking day. Heavy drinking is defined as five or more drinks or four or more drinks in a day for men and women, respectively.

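### Two current lists of primary outcomes disagree, and the SAP contains no analysis of script-induced craving or of treatment by PTSD status, which together are the title question

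*Combined protocol and SAP*

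**What the plan says.** The Statistical Analysis Plan section sets its scope as follows: "Statistical analysis will focus on three primary outcomes and a secondary outcome (average drinks per drinking day"). It then names the primaries: "The three primary outcomes are Percent Drinking Days (PDD), Percent Heavy Drinking Days (PHDD), and craving scores from PACS". It has one hypothesis-testing model, an intent-to-treat linear mixed regression on treatment by visit. Visit has two levels, before and after treatment, and participant is a random effect. Type 1 error is .05 per outcome. The only further interaction is pretreatment outcome by visit, which is exploratory.

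The Study Instruments table has its own Primary Outcomes block with five rows:
- "Alcohol Biomarker (Peth"), tagged as an outcome without an aim
- "Alcohol Craving (DAQ"), Aim 2
- alcohol use, Aim 2, with no metric given
- "Reward Craving for Craving Inductions from DAQ", Aim 1
- "Relief Craving for Craving Inductions from DAQ", Aim 1

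"Penn Alcohol Craving Scale" sits in the eligibility and blocking part of the table. It is scheduled at V1, V2 and V8, but its only stated purpose is inclusion. Screening Procedures gives it the same role: "a score of at least 10 is required". Form-90, from which the SAP computes PDD and PHDD, is listed among the secondary measures, though it is tagged as an outcome there. The CAPS is tagged as a blocking variable and as a treatment moderator for Aim 3, and the Randomization paragraph confirms blocking on PTSD status.

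**The concern.** Both lists are current text in the same document; neither is an amendment history. They point to different confirmatory results.

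The larger problem is what the SAP leaves out. The title asks how the two drugs affect craving induced by personalised scripts, in people with and without PTSD. The trial writes individual scripts, runs two counterbalanced inductions and blocks randomisation on PTSD, yet the SAP mentions neither the inductions nor PTSD. Several defensible analyses of the induction ratings exist, differing in item-to-script pairing, use of the pre-script score, handling of order, and model. Without a prior choice, that selection could be made after the data are seen.

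**Working it through.** No power calculation or effect size is given, so there is no figure to reproduce. The check is a comparison of the two lists and of each outcome's visits with the SAP model.

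| Outcome | Study Instruments table | Named in SAP | Can use the pre/post-treatment model |
|---|---|---|---|
| PDD, PHDD | Not by name; may be measures of alcohol use | Primary | Yes |
| PACS | Inclusion only (V1, V2, V8) | Primary | Yes |
| General DAQ | Primary block (V8); V2 and V8 in another row | No | Yes, if V2 is used |
| PEth | Primary block (V1, V8) | No | Yes |
| Induced reward craving | Primary block (V8) | No | No |
| Induced relief craving | Primary block (V8) | No | No |

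**Counts.** The table has 5 primary rows. One (alcohol use) has a SAP analysis if PDD and PHDD measure it, so 5 − 1 = 4 are not named. Of those 4, 2 fit the existing model and 2 do not. Of the 3 SAP primaries, 1 (PACS) is not an outcome in the table.

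**Why the model fails for induced craving.** It needs a value before treatment and one after. Craving Induction Procedures places all the ratings at the final visit, before and after each script. The pre-script rating is therefore not a pre-treatment value, because participants have by then had about six weeks of medication.

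**DAQ visits.** One table row gives V2 and V8; the Primary Outcomes row gives V8 alone. Baseline Assessment has the DAQ completed at Visit 2, so a pre-treatment value is planned, but the rows need reconciling.

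**PTSD.** The SAP has no treatment-by-PTSD term. Its pretreatment-outcome-by-visit interaction is not moderation of treatment by PTSD. Self-report Details says potential moderators will be looked at and gives no method.

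**Illustration of precision for treatment by PTSD.** Assumptions: 120/4 = 30 per arm (no allocation ratio is stated), no dropout, a proportion p of 30% to 50% with PTSD, no covariate adjustment and no multiplicity adjustment. In SD units, for n per side, SE = √[2/(np) + 2/(n(1 − p))], and the 95% half-width is about 1.98 × SE.
- One arm against double placebo, n = 30: p = 0.5 gives √(2/15 + 2/15) = 0.516, half-width 1.02; p = 0.3 gives √(2/9 + 2/21) = 0.563, half-width 1.12.
- One drug against no such drug across the 2×2 layout, n = 60, assuming the two drugs do not interact: p = 0.5 gives √(2/30 + 2/30) = 0.365, half-width 0.72; p = 0.3 gives √(2/18 + 2/42) = 0.398, half-width 0.79.

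These figures only explain the low-precision label proposed below. The finding does not depend on them.

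**The case against.** The best defence is that the SAP section governs: it says plainly which three outcomes are primary, and the table is an instrument list that may be partly out of date. The PACS cell could simply not have been updated. This has force, and a stale table could explain more than that one cell. It does not explain why the title, Design Overview, induction procedures and blocking still centre on induced craving and PTSD. The SAP also does not say that it covers only part of the trial.

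Some stronger readings are tempting, but the documents do not support them:
- **DAQ and PEth have no usable method.** The SAP introduces its mixed model for hypotheses in general, and both outcomes fit it. What is missing is their naming and rank.
- **The alpha rule covers only three primaries, or the plan tests every outcome in both lists as primary.** The rule is .05 for each outcome without such a limit, and no document proposes the combined list. A family-wise error rate for that union would describe no stated plan.
- **The SAP list was chosen after results were known.** Nothing in the documents shows when it was chosen relative to unblinding.
- **Every listed moderator needs a confirmatory model.** Self-report Details calls them potential moderators. Only PTSD is tied to both the title and the blocking.

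**Conclusion.** The point stands and must be fixed. Two current primary lists conflict, overlapping at most on alcohol use. Two table primaries, induced reward and relief craving, have no SAP analysis and cannot use the one provided; treatment by PTSD status has none either. Two more, general DAQ and PEth, lack only naming and rank. This rests on direct reading and counting, with one interpretive assumption: that PDD and PHDD measure the table's alcohol use. The document cites Aims 1 to 3 but does not set them out, so which outcomes should be primary, and which induced-craving analysis should lead, is for the sponsor to settle against those aims.

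**What to change.** 1. Issue one dated SAP version, before unblinding if possible and otherwise labelled post hoc, with a single list of primary and secondary outcomes. Place induced relief craving, induced reward craving, PDD, PHDD, PACS, general DAQ and PEth in it. Reconcile the DAQ visits and confirm that .05 per outcome applies to that list.
2. For induced craving at Visit 8, compare the four arms on DAQ relief items after the relief script and reward items after the reward script. Include induction order and the three blocking factors, and use the SAP's single-step confidence intervals. Report results with and without the pre-script score, and name the main analysis in advance according to the trial's aims. That score is measured after randomisation, so adjusting for it may remove part of the treatment effect.
3. For the primary outcomes, report treatment by PTSD status (Visit 1 CAPS) with 95% confidence intervals, labelled low precision. Do not claim absence of a difference from a non-significant test. Declare all other moderators exploratory.
4. Analyse general DAQ and PEth with the existing pre/post model.

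Alternatively, state that this SAP covers only the drinking and PACS outcomes, and supply the induced-craving and PTSD analyses in a separate dated document.

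The cost is SAP wording and analysis time. Every measure needed is already scheduled at V1, V2 or V8.

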"Effect of Prazosin and Naltrexone on Personalized Script Induced Alcohol Craving in Individuals with Alcohol Use Disorders with and without Comorbid PTSD" NCT02322047

PaN Study Protocol (8-17-2020)

Design Overview

This is a 7-week double-blind, double-dummy, placebo controlled study of prazosin and naltrexone for Veterans with an AUD that includes two imaginal craving inductions at the final study visit, one oriented towards relief craving and the other towards reward craving. After passing an initial telephone screen, participants are seen for an in-person eligibility appointment that includes a physical and psychiatric examination, labs, and self-report measures. One hundred twenty individuals who meet study inclusion/exclusion criteria will enter the medication phase of the study within 14 days of the initial assessment initiating prazosin/placebo as well as 50mg naltrexone/placebo treatment. Randomization is blocked by gender, PTSD status, and desire to abstain vs. desire to cut down. Prazosin is titrated to three times daily dosing (9 am: 4mg; 3pm: 4 mg; 9pm: 8mg) at the end of two weeks. Naltrexone is taken once daily 50 mg/day with no titration schedule. The stable dose of both medications continues for four more weeks and medication compliance is evaluated through pill counts and riboflavin trace in urine analysis. On approximately day 42 participants come into the lab for the craving inductions (there is a two-week window after day 42 in which participants may still be seen if scheduling issues arise). The order of the craving inductions is counterbalanced, and their administration separated in time by 30 minutes to minimize carry over between them. Subjective responses to the craving inductions is obtained via relief oriented craving items and reward oriented craving items from the Desire for Alcohol Questionnaire. Participants are then assisted in returning their craving levels to baseline prior to debriefing. They are all offered DoD, VA, or community referrals to treatment. Both prazosin and naltrexone can be safely discontinued without tapering.

Setting, Recruitment, Participants, and Inclusion/Exclusion Criteria

Study Setting:

There are three VAPS study sites including the Seattle Division VA, the American Lake Division VA, and the Mt Vernon CBOC VA. Clinical backup in case of emergencies is available at all sites.

Participants and Recruitment:

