Laboratory Procedures: Women of childbearing potential provide urine for a pregnancy test at screening and again at weeks 4 and 8. Laboratory evaluation of blood samples includes CBC, routine liver function tests, and routine serum chemistries. Specimens are also sent to a lab in Minnesota, MedTox, for assessment of the alcohol biomarker phosphatidylethanol – Peth. The lab procedure differs slightly by site as follows: Seattle VA: The Clinical Research Unit (CRU) draws the blood samples and ship the specimens to MedTox. Either the Clinical Research Unit (CRU) or study staff deliver the remaining vial(s) to the Seattle VA lab for processing. Study participants are escorted by study staff to the CRU at the end of the initial study visit.

American Lake VA: Clinical Studies Unit staff (CSU) draws the blood samples and ships the specimens to MedTox. A member of the Clinical Studies Unit (CSU) or study staff delivers the remaining vial(s) to the lab for processing. Study participants are escorted by study staff to a room in the CSU at the end of the initial study visit.

Mt. Vernon CBOC VA:Blood specimens are drawn by lab personnel in the on-site lab. Specimens are then transported to the Seattle VA via a courier service. Mt Vernon CBOC VA specimens for MedTox are held at an identified location in the Seattle VA lab and then picked up by Clinical Research Unit (CRU) staff to be shipped to MedTox.

Safety and Comfort Call by Study RA (Safety and & Comfort Call #1): The RC calls the participant the next business day following the initial screen to assess any symptom exacerbation stemming from the visit, to provide support.

Randomization, Baseline Assessment, and Initial Medication Administration (Visit 2; Study Day 8):

Randomization: In this double-blind, double-dummy design participants are randomized to one of four study conditions: prazosin + naltrexone; prazosin + naltrexone placebo; naltrexone + prazosin placebo, and double placebo. Randomization is blocked by gender, PTSD status, and alcohol consumption goal (abstention vs. reduction). Random assignment to study condition is conducted by the VAPSHCS Research Pharmacist with randomization tables supplied by the study PIs. The Research Pharmacist distributes study medications appropriate to the randomization condition. The Research Pharmacist will have no contact with participants. Study medications will have been prepared ahead of time and will be available at Study Visit 2.

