Hypotheses will be tested using intent-to-treat (ITT) linear mixed effect analyses. Specifically, differences in outcome measures from pre-treatment through the study medication phase will be estimated using linear mixed effects regression of outcome (the dependent variable) on treatment by study visit interaction (the independent fixed effects). Study visit will be modeled as categorical (post- vs. pre-treatment). Study participant will be modeled as a random effect. Model results will be summarized with estimated marginal means at pre- and post-treatment for each treatment group, within-group mean change from pre-treatment and mean difference in change by group. The latter set of means will also be presented as standardized effect sizes calculated using the standard deviation of the outcome at baseline as the denominator. Hypothesis testing for the overall difference in change in outcome by treatment will be carried out using the likelihood ratio test for the significance of the study visit by treatment interaction term. All means will be accompanied by standard errors, and all mean differences will also be presented with 95% confidence intervals (CIs), which will be adjusted for the four sets of differences estimated corresponding to the four treatment groups using the single-step method.

Exploratory analyses will be carried out to separate the effect of the treatment from the effect of the pretreatment levels of each outcome on the estimates of post-treatment change in outcomes by adding a pretreatment outcome by visit interaction term to the model. Descriptive analyses will be carried out to summarize clinical outcomes at the last week of study. Lower risk drinking will be defined using NIAAA guidelines; for men this means exceeding neither 14 drinks per week nor 4 drinks per day and for women this means exceeding neither 7 drinks per week nor 3 drinks per day. The number of abstinent drinking days and the number of participants who are completely abstinent during the last week will also be computed. Additionally, both the raw mean PDDs and PHDDs will be computed for each week of study medication and plotted by group to illustrate changes over time in these outcomes. Type 1 error will be set at .05 for each outcome. Analyses will be carried out using R 3.6.2, and the packages lme4, emmeans and tidyverse.

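### Randomisation is blocked by gender, PTSD status and drinking goal, but the primary mixed model uses none of them; some precision may go unused (minor, cheap to fix)

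*Combined protocol and SAP*

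**What the plan says.** The Design Overview states: "Randomization is blocked by gender, PTSD status, and desire to abstain vs. desire to cut down". The Randomization paragraph for Visit 2 repeats it: "Randomization is blocked by gender, PTSD status, and alcohol consumption goal (abstention vs. reduction".

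The Statistical Analysis Plan gives the primary model as "linear mixed effects regression of outcome (the dependent variable) on treatment by study visit interaction (the independent fixed effects". Visit has two levels, before and after treatment, and participant is the only random effect. On the test it says: "Hypothesis testing for the overall difference in change in outcome by treatment will be carried out using the likelihood ratio test" of the visit by treatment term. The one extension is exploratory and adds a pre-treatment "outcome by visit interaction term to the model".

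The Study Instruments table gives alcohol use goal the purposes "inclusion, blocking, treatment moderator" and the CAPS the purposes "blocking, treatment moderator (Aim 3"). The Statistical Analysis Plan contains no moderator model, so these labels do not bring the factors into any specified analysis.

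**The concern.** Blocking makes the arms alike on the three factors. An analysis that ignores them still counts the variation they explain as noise, so the balance that was designed in is not credited in the standard errors.

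The tested quantity here is within-person change. A factor that shifts the outcome equally at both visits cancels out and costs nothing. Only a factor that predicts change matters.

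Drinking goal is the most plausible such factor for percent drinking days and percent heavy drinking days. According to Screening Procedures, the questionnaire "includes a forced choice item regarding their goals for their alcohol use over the next month", and those two outcomes measure drinking during the weeks that follow. The documents give no comparable reason to expect gender or PTSD status to predict change, or any of the three to predict change in PACS craving.

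At stake are over-wide standard errors and some lost power in a four-arm trial of 120 people.

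**Working it through.** **Inputs from the documents.** 120 randomised (Participants and Recruitment); four arms (Randomization); two visit levels, a 3-df likelihood ratio test and alpha .05 per outcome (Statistical Analysis Plan). There is no power calculation to reproduce.

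**Assumptions.** 30 per arm, complete pre/post pairs, approximately normal changes with equal variance, and blocking that achieves balance. R2 is the share of change variance explained by the three factors. The documents give no R2, allocation ratio, block size, factor prevalence or dropout rate.

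**Step 1: reduce to change scores.** With complete pairs, and a participant variance estimated above zero, the test of treatment by visit is a comparison of change scores. The likelihood ratio statistic is N × log(RSS0/RSS1), where RSS0 and RSS1 are the residual sums of squares without and with treatment. On one simulated data set this and a maximum-likelihood mixed model both gave 1.3857. Adding a main effect of goal left it at 1.3857; adding goal by visit moved it to 1.7090. Main effects alone therefore do nothing.

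**Step 2: standard errors.** Overstatement = 1/sqrt(1 - R2) - 1. At R2 = .10: 1/sqrt(.90) = 1.054, or 5.4%.

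**Step 3: size of the unadjusted tests.**
- F test: P(F(3,116) > 2.683/(1 - R2)).
- Planned test: it rejects when the statistic exceeds 7.815, that is, when F > (exp(7.815/120) - 1) × 116/3 = 2.602. Its size is P(F(3,116) > 2.602/(1 - R2)), which equals .05 at R2 of about .030.
- Likelihood ratio test with the three added terms: the cut-off falls to (exp(7.815/120) - 1) × 113/3 = 2.535 on F(3,113), giving size .060.

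**Step 4: power.** A noncentrality of 11.277 gives 80% on F(3,116).
- Unadjusted: P(ncF(3,116; 11.277/(1 - R2)) > 2.683/(1 - R2)).
- Adjusted: P(ncF(3,113; 11.277/(1 - R2)) > 2.685).
- The last column repeats the comparison with the planned likelihood ratio test as the starting point, set to 80% on its own cut-off (noncentrality 10.952).

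| R2 | SE overstated | Size, unadjusted F | Size, planned LRT | F power, unadjusted v adjusted | Full change v planned LRT (points) |
|---|---|---|---|---|---|
| 0 | 0% | .050 | .055 | .800 v .7996 | -1.3 |
| .02 | 1.0% | .047 | .052 | .800 v .808 | -0.5 |
| .05 | 2.6% | .042 | .047 | .801 v .822 | +0.8 |
| .10 | 5.4% | .034 | .038 | .803 v .844 | +2.9 |
| .20 | 11.8% | .021 | .024 | .806 v .887 | +7.1 |

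A simulation supports these figures. It used 30,000 runs per setting and permuted blocks of 4 within eight strata, assuming 10% women, 50% PTSD, 40% aiming to abstain, and all R2 from goal. Planned-test size was .056, .052, .047, .036, .026. With the added terms, likelihood ratio size was .059 to .062 and adjusted F size was .048 to .051.

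**Step 5: what these R2 values require.** If goal alone supplies R2 and a share q aims to abstain, the two goal groups must differ in mean change by sqrt(R2/(q(1 - q))) SD. At q = .40 this is 0.29, 0.46, 0.65 and 0.91 SD for R2 = .02, .05, .10 and .20. For q from 20% to 50% the ranges are 0.28-0.35, 0.45-0.56, 0.63-0.79 and 0.89-1.12 SD.

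**The case against.** The planned model is simple and valid. The estimate is unbiased, the documents do not contradict themselves here, and any loss depends on an R2 they do not supply. All of that stands, and it is why the point is minor. R2 = .20 would need a gap of about 0.9 SD between goal groups, which nothing in the documents supports, so it is only the top of an illustrative range.

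It is also fair that comparing two F tests flatters the change, because the plan uses a chi-square likelihood ratio test. Against that test the full change loses up to 1.3 points when R2 is below about .03. That loss comes almost wholly from removing size above .05: the planned test has size .055 at R2 = 0, and moving to F alone costs about 1.3 points.

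If blocking failed and balance arose only by chance, the cost at R2 = 0 would be larger. Power would fall from .800 to about .788 against the F test, or about .775 against the planned test (noncentrality multiplied by 1 - 3/119).

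Finally, percent drinking days and percent heavy drinking days are bounded, so the third decimals above should not be taken literally. None of this explains why factors important enough to block on are absent from the analysis.

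**Conclusion.** The point holds as a minor one. The primary model omits all three blocking factors and the plan gives no reason. This is an efficiency gain left unused; it does not threaten validity.

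The gain is nil or slightly negative below R2 of about .03, small at .05, and worth about 3 points at .10. In sample-size terms, R2 = .10 is equivalent to 30/(1 - .10) = 33.3 per arm instead of 30. The case is strongest for goal on the two drinking outcomes and unsupported by the documents for PACS. All sizes rest on an assumed R2, equal arms, complete pairs and achieved balance.

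**What to change.** In the primary model for each outcome, add gender, PTSD status and drinking goal as additive terms, each with its visit interaction. Use the values on which randomisation was done; this should be stated, since Screening Procedures places the goal item in the demographic questionnaire and the Study Instruments table places it in the MINI. Three additive terms are safer than all 2 × 2 × 2 = 8 cells, some of which may be sparse.

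Test the 3-df visit by treatment term against an F distribution, for example with Kenward-Roger degrees of freedom. Adding the terms while keeping the chi-square reference would raise the size to about .060.

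The cost is two SAP sentences and 3 degrees of freedom for the change contrast (116 to 113). All three factors are already recorded at V1. An ANCOVA of the post-treatment value with the same factors is another route, but it would make baseline adjustment primary and the figures above do not describe it.

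If the simpler model is preferred, one sentence saying why the blocking factors are omitted would be enough.

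### As naturally read, the primary mixed model assumes one outcome variance before and after treatment, so the planned standard errors of the visit means will be wrong if the two variances differ

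*Combined protocol and SAP*

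**What the plan says.** The Statistical Analysis Plan names three primary outcomes: Percent Drinking Days (PDD), Percent Heavy Drinking Days (PHDD) and the PACS craving score. Each is modelled on the treatment-by-visit interaction. On visit the plan says "Study visit will be modeled as categorical (post- vs. pre-treatment"), and on the random part only that "Study participant will be modeled as a random effect". On software it says "Analyses will be carried out using R 3.6.2, and the packages lme4, emmeans and tidyverse". No residual variance structure, robust standard error or missing-data method is given beyond the intent-to-treat label.

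The reporting commitments are specific: "Model results will be summarized with estimated marginal means at pre- and post-treatment for each treatment group", together with within-group change and difference in change, and "All means will be accompanied by standard errors, and all mean differences will also be presented with 95% confidence intervals (CIs"). The hypothesis test is a likelihood ratio test of the interaction.

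Three other statements bear on the variances:

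- PDD and PHDD come from Form-90 "drinking data for the three months prior to receipt of study medication as well as the six-weeks of study medication" (Statistical Analysis Plan).
- For PACS at screening, "a score of at least 10 is required" (Screening Procedures).
- The inclusion criteria also set a minimum level of recent drinking. Neither minimum applies at the final visit.

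**The concern.** A random intercept plus a single residual variance implies Var(pre) = Var(post), and the same total variance in every arm. Four features of the design work against that:

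- the PACS floor trims the lower tail at entry only;
- the drinking minimum does the same for drinking, whereas participants may later be anything from abstinent to unchanged;
- PDD and PHDD average over about 90 days before treatment and about 42 days on it;
- four different treatments act only on the later value.

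If the variances differ, the standard error attached to each visit mean comes from a pooled variance that fits neither visit. If post-treatment values are also missing, the likelihood uses the wrong regression of post on pre to account for them, which can affect the primary test and the difference in change. Missing final values are foreseeable, because the visit procedures allow participation to be terminated for side effects. No dropout rate is stated.

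**Working it through.** The plan gives no SD, pre/post correlation, dropout rate or power calculation, so there is no figure of its own to reproduce. Inputs from the documents: 120 randomized, four arms, two visits. Assumptions: 30 per arm (allocation is not stated), pre SD 1, post SD r, correlation 0.5.

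**Visit means, complete data.** The random-intercept model uses V = (1 + r²)/2 at both visits. Its SE is √(V/n), against a true 1/√n before and r/√n after. Model SE over true SE is therefore √V before and √V/r after.

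| r | V | pre | post | coverage of nominal 95% interval, post |
|---|---|---|---|---|
| 0.7 | 0.745 | 0.86 | 1.23 | 98.4% |
| 1.0 | 1.000 | 1.00 | 1.00 | 95.0% |
| 1.1 | 1.105 | 1.05 | 0.96 | 93.9% |
| 1.2 | 1.220 | 1.10 | 0.92 | 92.9% |
| 1.4 | 1.480 | 1.22 | 0.87 | 91.1% |

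For example, with n = 30 and r = 1.4 the true post SE is 1.4/√30 = 0.256, and the model reports 1.217/√30 = 0.222.

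**Change, complete data.** The model variance of change is 2(V − cov) = 1 + r² − 2cov, which is the true value at every r. In simulation (4,000 runs per setting, equal arm variances, r from 0.7 to 2) the likelihood ratio test rejected a true null in 4.8 to 5.9% of runs, and coverage for a difference in change was 94.0 to 95.0%.

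**Missing post-treatment values.** The model regresses post on pre with slope cov/V instead of cov/Var(pre). At r = 1.4 this is 0.7/1.48 = 0.47 instead of 0.70. Simulated results:

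- *Missing completely at random:* no material bias. Type I error was 7.0% at r = 1.5 and 9.0% at r = 2 (base rate 20%). A separate run with 25% missing (1,500 runs) gave 8.1%, 7.6% and 9.7% at r = 1.4, 1.5 and 2, against 5.7% at r = 1. Monte Carlo error is about 0.4 to 0.7 percentage points. At r = 0.7 the test was slightly conservative (4.4%).
- *Missingness rising with baseline, same in all arms (about 24%):* the within-arm change is biased by 0.035, 0.00, −0.068 and −0.127 baseline SD at r = 0.7, 1, 1.5 and 2. The difference between arms has bias near 0.
- *Missingness rising with baseline and differing by arm (about 33/24/24/13%):* bias in the difference is 0.028, 0.00, −0.052 and −0.097 SD at the same ratios, and type I error is 4.6%, 6.0%, 8.3% and 9.6%. Separate runs at r = 1.4 gave about 0.05 SD, and at 1.1 to 1.2 about 0.005 to 0.016 SD.
- *Free two-visit covariance, missingness rising with baseline (same in all arms, or differing by arm), r = 0.7, 1.5 and 2:* bias in the difference between −0.011 and 0.005 SD, coverage 94.3 to 95.2%.

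**What ratio is plausible?**

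- *PACS.* Assume a normal score with mean 14 to 18 and SD 6 to 7. Truncation at 10 cuts the SD to 4.4 to 5.7. If the screening value is the pre row and no trace of selection remains at the final visit, the ratio is 1.17 to 1.41. If the Visit 2 value is used, with a V1–V2 correlation of 0.6 to 0.8, it is 1.05 to 1.21. The Study Instruments table lists PACS at V1, V2 and V8, and the plan does not say which is the pre value.
- *Look-back windows.* With between-person SD s = 0.2 to 0.3 and p = 0.4 to 0.6, √[(s² + p(1−p)/42)/(s² + p(1−p)/90)] is about 1.02 to 1.04, or 1.05 to 1.09 if day-to-day clustering triples the sampling variance.

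**The case against.** The strongest reply is that the plan tests only the interaction, and with complete data and equal arm variances that test and both kinds of change estimate are correct whatever the ratio. This stands. The certain damage is confined to the standard errors of the visit means, which are summaries. A reader might infer that the primary test is invalid as planned, and the documents do not support that.

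Second, a reader might infer that missing final values by themselves bias the treatment comparison. They do not. Bias in the difference needs unequal variances, missingness related to baseline, and a missingness pattern (or variance) that differs by arm.

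Third, the direction is not given. Selection at entry suggests a larger post-treatment variance, but PDD and PHDD are bounded and reductions toward zero could shrink it. The window lengths alone contribute little, and a Visit 2 PACS baseline would put the ratio nearer 1.1.

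Fourth, lme4 is not strictly confined to equal variances. With visit coded 0/1, `(1|id) + (0+visit|id)` gives the same log-likelihood as an unstructured model when the SD ratio is 1.4. At 0.7 it goes singular and fits worse (−295.5 against −287.7). So the package does not rule out a better model, but the plan's wording does not ask for one.

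Finally, the documents give no arm-specific SDs. With complete data and post SD assumed to be 1.5 in both compared arms and 1.0 in the other two, pairwise coverage was 91.9%. In the other unequal-arm settings tried it was 93.6 to 95.0%, and type I error across all of them was 5.3 to 6.0%.

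**Conclusion.** The point holds in limited form. On its natural reading the model imposes equal variance at both visits and in all arms, the design gives reason to doubt this, and the plan commits to reporting standard errors that depend on it. Those errors are modest near a ratio of 1.1 and material by 1.4, and they reverse below 1. Effects on the primary test (type I error roughly 7 to 9%, highest single run 9.7%) need missing final values and a ratio of about 1.4 to 2. Bias in the difference in change (about 0.05 to 0.10 baseline SD at those ratios, negligible at 1.1) also needs missingness that depends on baseline and differs by arm. Every ratio, the 0.5 correlation, equal allocation and the dropout rates are assumptions. The single residual variance is itself inferred from the two-visit model and the named package, since the plan does not state it. This is a cheap improvement, not a flaw that invalidates the primary analysis.

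**What to change.** Keep the fixed effects and the estimand, and state in the Statistical Analysis Plan that the two visits have an unstructured covariance. One implementation is `nlme::gls` with `corSymm` by participant and `varIdent` by visit. It works whichever visit is more variable, and emmeans accepts it. If the team prefers to stay in lme4, an added post-visit random effect gives the same fit only when the post-treatment variance is at least the pre-treatment variance and the covariance is positive. Arm-specific variances, or robust standard errors for the pairwise intervals, can be an optional sensitivity analysis.

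The cost is a sentence or two of wording, one extra variance parameter, one more package on the list, and slightly wider intervals if the variances turn out to be equal. With complete data the change estimates do not alter.
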